8.4.2.3.3 Unanticipated Problems

Unless otherwise specified above, UPs that are also AEs or SAEs, must be reported to the CSO (by REDCap, or by email and SERF if REDCap is not available) no later than when they are due to be reported to the IRB.

UPnonAEs are not reported to the CSO but must be reported to the clinical trials management (CTM) group and the IRB according to their requirements and preferred methods. If the UPnonAE raises a significant potential subject safety concern, the SMM should be consulted by email or phone no later than when the report is made to CTM.

8.4.2.3.4 Pregnancy

Pregnancy testing will be performed prior to the first study vaccination. If the result is positive, the participant will be withdrawn from the study, and no additional follow-up will be performed.

8.4.2.4 Sponsor's Reporting Responsibilities

Events reported to the sponsor will be promptly evaluated and will be reported as required according to FDA IND safety reporting guidance and regulations. IND safety reports will be sent to other investigators conducting research under the same IND and will be shared with other stakeholders according to applicable agreements (e.g., CRADAs and CTAs).

The sponsor will also submit an IND annual report of the progress of the investigation to the FDA as defined in 21 CFR 312.33.

All UPs will be evaluated by the sponsor, and a summary of the event, and any necessary (corrective/preventative) actions, will be distributed to investigators conducting research under the same IND as may be relevant and appropriate.

8.4.3 Withdrawal Criteria for an Individual Subject

An individual subject will be withdrawn from the study for any of the following:

- An individual subject's decision. (The investigator should attempt to determine the reason for the subject's decision.)
- Non-compliance with study procedures or requirements (see sections [5.5](#) and [6.5](#)) to the extent that it is potentially harmful to the subject or to the integrity of the study data, per investigator discretion.
- The investigator determines that continued participation in the study would not be in the best interest of the subject.

The reason for participant withdrawal will be recorded in the research database.

8.4.3.1 Re-enrollment and Unplanned Procedure Repetition

Unless otherwise specified within this protocol, each person who is a subject in this study may be enrolled, and may pass through each step and process outlined in the protocol, only **ONCE** (i.e., subjects may not “go back” and repeat a protocol step already completed). On a case-by-case basis, a request for re-enrollment, or for repetition of a protocol step or procedure already

completed, may be submitted to, reviewed by, and approved by the SMM in writing. The SMM may also recommend or require consultation of the IRB and/or DSMB.

8.4.3.2 Replacement of Withdrawn Subjects or Subjects Who Discontinue Study Agent

Subjects who are withdrawn from the study or discontinue study vaccinations will not be replaced.

All subjects exposed to study agents must be included in the safety dataset.

8.4.4 Additional Safety Oversight

8.4.4.1 Safety Review and Communications Plan

A safety review and communication plan (SRCP) is required for this protocol. The SRCP is an internal communications document between the principal investigator and the CSO, as sponsor representative, which delineates key safety oversight responsibilities of the principal investigator, the CSO, and other stakeholders. The SRCP includes a plan for conducting periodic safety surveillance assessments by the CSO.

8.4.4.2 Sponsor Medical Monitor

A SMM, representing the sponsor, has been appointed for oversight of safety in this clinical study. The SMM will be responsible for performing safety assessments as outlined in the SRCP.

8.4.4.3 Oversight Committees

8.4.4.3.1 Data and Safety Monitoring Board

The NIAID intramural data and safety monitoring board (DSMB) includes independent experts that do not have direct involvement in the conduct of the study and have no significant conflicts of interest as defined by NIAID policy. The DSMB will review the study protocol, consent document, and investigator brochure prior to initiation and twice a year thereafter, or as may be determined by the DSMB. In addition, the DSMB will review unblinded data after the first 5 participants complete study vaccinations or after the first 4 months (whichever comes first), and every 4 months thereafter (or after every 20 participants completes study vaccinations, whichever comes first). The DSMB can make a variety of recommendations, such as: 1) stop the trial because of safety concerns, either based on the halting rules or based on results that are similarly concerning to those established in the halting rules, 2) stop the trial if there appears to be little value in proceeding (e.g., inability to recruit participants or if no reactions occur after, perhaps, 40 subjects have been evaluated), 3) continue the trial, but announce the topline interim results to the public, if timely release of the data will provide important guidance to the community, or 4) continue the trial without modification.

The DSMB may convene additional reviews as necessary or per principal investigator request to evaluate the safety, efficacy, study progress, and conduct of the study.

All deaths, SAEs, UPs, pregnancies, and IND safety reports will be reported to the DSMB at the same time they are submitted to the IRB and CSO unless otherwise specified herein. A summary of PSEEs will also be provided for review by the DSMB along with study documents submitted for periodic scheduled DSMB reviews.

All cases of intentional or unintentional unblinding will be reported to the DSMB not later than one business day from the time of study personnel awareness.

The principal investigator will notify the DSMB at the time pausing or halting criteria are met and obtain a recommendation concerning continuation, modification, or termination of the study. The principal investigator will submit the written DSMB summary reports with recommendations to the IRB.

8.4.5 Pausing Rules

“Pausing” is discontinuation of study vaccinations in a single subject. Other than discontinuation of study vaccinations, subjects will continue to be followed per protocol during a pause.

The pausing criterion for individual subjects in this study is the following:

- A subject experiences CoFAR Grade 4 allergic reaction to the first study vaccination.
- A subject experiences an ESI or an SAE assessed as being caused by the vaccine/placebo (unless the event is a PSEE).

The principal investigator or the CSO may also pause dosing/study interventions for one or more subjects for any safety issue. The DSMB may recommend a pause to the CSO.

8.4.5.1 Reporting a Pause

If a pausing criterion is met, a description of the AE(s) or safety issue must be reported by the principal investigator within 1 business day to the CSO and the IRB according to their requirements. The principal investigator will also notify the DSMB.

8.4.5.2 Resumption Following a Pause

If the pausing criterion is met following the first study vaccination, the second study vaccination will not be administered to that participant, but the other remaining study procedures will proceed as scheduled. The CSO, in collaboration with the principal investigator and DSMB or other safety review entity, will determine if any additional modifications or requirements may apply, for the impacted subject(s), or whether the events that triggered the pause require expansion to a study halt (see below).

The CSO or sponsor designee will notify the principal investigator of the decision. The principal investigator will notify the IRB of the decision according to the IRB’s process.

8.4.5.3 Discontinuation of Study Agent

Discontinuation of study vaccination does not mean discontinuation from the study, and remaining study procedures may be completed as indicated by the study protocol if the subject is willing to remain on study.

8.4.6 Halting Rules for the Protocol

“Halting” is discontinuation of study vaccinations for all subjects in a study and suspension of enrollment until a decision is made to either resume or permanently discontinue such activity.

Subjects who have already received a study vaccination at the time of a halt will continue to be followed per protocol.

The halting rules are:

- More than 3 subjects experience a CoFAR Grade 4 allergic reaction and the frequency of Grade 4 allergic reactions is more than 10% of subjects enrolled to date;
OR
- Any safety issue that the principal investigator or the CSO determines should halt the study. The DSMB may recommend a halt to the CSO;
OR
- Any death.

In addition, the FDA or any regulatory body having oversight authority may halt the study at any time. The DSMB may recommend a study halt.

8.4.6.1 Reporting a Study Halt

If a halting criterion is met, a description of the AE(s) or safety issue must be reported by the principal investigator within 1 business day to the CSO and the IRB according to their requirements. The principal investigator will also notify the DSMB.

8.4.6.2 Resumption of a Halted Study

If a halting criterion is met, enrolled subjects who have received a study vaccination will continue with the remaining study procedures (other than study vaccinations) as scheduled. The principal investigator, CSO, and DSMB will discuss the option of continuing the study but administering the study agent in graded doses (10% of full dose, observe 30 minutes, and then administer remaining dose), or whether any other study modifications should be made.

The CSO or sponsor designee will notify the principal investigator of the decision. The principal investigator will notify the IRB of the decision according to the IRB's process.

8.4.6.3 Discontinuation of Study

The study will be stopped permanently for a single Grade 5 reaction. Subjects will continue to be followed for protocol-specified safety assessments or as clinically indicated, whichever is more conservative.

8.5 UNANTICIPATED PROBLEMS.

8.5.1 Definition of Unanticipated Problems

The definition of a UP is provided in section [8.4.1](#).

8.5.2 Unanticipated Problem Reporting

The investigator will report UPs to the NIH IRB as per Policy 801.

8.5.3 NIH Intramural IRB Reporting of IND Safety Reports

Only IND Safety Reports that meet the definition of a UP will need to be reported to the NIH Intramural IRB.

9 STATISTICAL CONSIDERATIONS

The analysis will be primarily aimed at estimation and description. There is considerable uncertainty about the number of subjects that can actually be enrolled, so both the sample size rationale and planned analysis are written to take that uncertainty into account. There is no intent to write a formal Statistical Analysis Plan.

9.1 STATISTICAL HYPOTHESIS

The primary goal is estimation of the primary and secondary endpoints, and estimation of the difference in endpoints between the active and placebo vaccines. Statistical hypothesis testing will be done to compare active versus placebo vaccines, but this is secondary to estimation.

The endpoints are as follows, and are defined in greater detail previously in the protocol (sections 1.1 and 3):

Primary Endpoint:

- Proportion with systemic allergic reaction to the active (ie, Pfizer-BioNTech) vaccine dose delivered in this study

Secondary Endpoints:

- Proportion with severe systemic allergic reaction to the COVID-19 vaccine dose delivered in this study
- Proportion with mild/moderate systemic allergic reaction to the COVID-19 vaccine dose delivered in this study
- Proportion with anaphylactic reaction to the COVID-19 vaccine dose delivered in this study
- Proportion with systemic allergic reaction to each study vaccination (i.e. active and placebo/pre- and post-crossover) by arm
- Proportion with more (or less) severe systemic allergic reaction to the COVID-19 vaccine dose delivered in this study than recorded reaction to the first full COVID-19 vaccine dose

9.2 SAMPLE SIZE DETERMINATION

The goal is to enroll up to 100 subjects; however, realistically, it may only be possible to enroll a smaller cohort. The ability to recruit for this study will depend on the rarity of such allergic reactions in the population and the acceptability of repeat vaccination and a 4-day hospital stay among individuals who have had these reactions. Current data indicates an extremely low systemic reaction rate, although it is likely that the overall rate may be higher since individuals recruited for this study have a history of a systemic allergic reaction following administration of the first dose of the vaccine. In sum, the study will provide more precise estimates with greater enrollment; however, even if fewer than 100 subjects enroll, the resulting data will provide valuable new information.

Since the primary goal of the study is estimation, we present the following example exact confidence intervals as a function of varying sample size and varying outcomes to illustrate achievable precision of estimates. We present such confidence intervals for the primary endpoint,

and also estimation of the risk difference of active vaccine versus placebo vaccine. The difference between active and placebo can be estimated in 2 different ways: one compares the results in the randomized arms at the first shot; and the other compares results within a subject across the 2 study vaccinations, exploiting the crossover design. Tables below present a subset of example scenarios in the study.

Table 5: Exact 95% Clopper Pearson Confidence Intervals for Primary Outcome, by Sample Size and Proportion with Systemic Allergic Reaction to Second Dose

Total N	Observed Reaction Rate					
	.00	.20	.40	.60	.80	1.00
5	0-0.522	0.005-0.716	0.053-0.853	0.147-0.947	0.284-0.995	0.478-1
10	0-0.308	0.025-0.556	0.122-0.738	0.262-0.878	0.444-0.975	0.692-1
15	0-0.218	0.043-0.481	0.163-0.677	0.323-0.837	0.519-0.957	0.782-1
20	0-0.168	0.057-0.437	0.191-0.639	0.361-0.809	0.563-0.943	0.832-1
40	0-0.088	0.091-0.356	0.249-0.567	0.433-0.751	0.644-0.909	0.912-1
60	0-0.06	0.108-0.323	0.276-0.535	0.465-0.724	0.677-0.892	0.94-1
80	0-0.045	0.119-0.304	0.292-0.516	0.484-0.708	0.696-0.881	0.955-1
100	0-0.036	0.127-0.292	0.303-0.503	0.497-0.697	0.708-0.873	0.964-1

As the sample size increases, precision in the estimate of the true proportion of subjects with a reaction to the second vaccine dose also increases. As an example, if the total N is 10, and there is .20 reaction rate (i.e., 2 react) to active vaccine, then the 95% CI for reaction rate is (.025, .556).

Table 6: Exact 95% Confidence Intervals for the Difference in Reaction Rate Between Vaccine and Placebo Arms on Day 1

Total N	Observed Reaction Rate per Arm on Day 1		
	1.00 Vaccine, .00 Placebo	.80 Vaccine, .20 Placebo	.60 Vaccine, .20 Placebo
6	0.082-1	-0.282-0.992	-0.554-0.889
10	0.383-1	-0.112-0.933	-0.268-0.858
20	0.663-1	0.127-0.862	-0.058-0.756
40	0.824-1	0.287-0.798	0.084-0.666
60	0.881-1	0.313-0.767	0.134-0.622
80	0.702-1	0.338-0.748	0.144-0.594
100	0.597-1	0.355-0.734	0.16-0.575

Note: If only 6 subjects are enrolled, a reaction rate of 80% in the vaccine arm corresponds to 3/3 reactions; a reaction rate of 60% in the vaccine arm corresponds to 2/3 reactions; and a reaction rate of 20% in the placebo arm corresponds 1/3 reactions.

Thus, if the total N is 20 with 10 on active vaccine on Day 1 and 10 on placebo, and 8 of those receiving active vaccine have a reaction and 2 of those receiving placebo have a reaction, the 95% CI for the excess reaction in active vaccine minus placebo is (.127, .862). Since this particular confidence interval does not include zero, this is also a demonstration that vaccines lead to excess reactions.

Table 7: Exact 95% Confidence Intervals for the Risk Difference Comparing each Individual's Vaccine Phase to Placebo Phase Response Using McNemar's Approach

Total N	Observed Reaction Rate per Treatment Phase		
	1.00 Vaccine, .00 Placebo	.80 Vaccine, .20 Placebo	.60 Vaccine, .20 Placebo
5	-0.044-1	-0.275-0.947	-0.369-0.853
10	0.338-1	0.04-0.878	-0.088-0.738
15	0.517-1	0.162-0.837	0.026-0.677
20	0.621-1	0.235-0.809	0.084-0.639
40	0.797-1	0.369-0.751	0.192-0.567
60	0.861-1	0.423-0.724	0.238-0.535
80	0.895-1	0.453-0.708	0.264-0.516
100	0.915-1	0.473-0.697	0.281-0.503

The examples above assume that if a subject reacts to the placebo phase, they will also react to the active vaccine phase. For example, with 10 subjects, and a reaction rate of 80% in the active vaccine and 20% in the placebo, this means that 2 subjects react to both active vaccine and placebo, 6 subjects react only to active vaccine, and 2 subjects react to neither. And, in this example the 95% confidence interval for excess reaction rate in active vaccine minus placebo is (.04, .878). The confidence intervals in this table are narrower than the ones in the previous table, since they use information from both study vaccinations. (There are other scenarios to get the same reaction rates [i.e. in the previous example, 1 subject reacts to both active vaccine and placebo, 7 subjects react only to active vaccine, 1 subject reacts only to placebo, and 1 subject reacts to neither], but these alternatives are not presented here, and the confidence intervals would be slightly different.)

While hypothesis testing will be done comparing active vaccine and placebo reactions, this goal is viewed as secondary to estimation of the difference.

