Prior to enrollment, participants will be screened remotely by phone/email and/or videoconference (using an NIH-approved platform) to assess eligibility and to ensure co-morbid allergic and other diseases, including asthma and atopic dermatitis, are well-controlled and disease activity is stable. If individuals have co-morbid conditions that may increase their risk of having a severe allergic reaction, they may be asked to come to the NIH CC for additional studies, such as pulmonary function testing, echocardiogram, or blood laboratory testing, that are felt to be clinically necessary (based on the discretion of the study team) to ensure that they are medically stable to undergo the study intervention. After screening, eligible individuals will be enrolled and admitted to the NIH CC ICU on day 0. Two IV lines will be inserted prior to study vaccination to allow for frequent blood draws and rapid administration of fluids/medications if needed in the event of a reaction. We will aim to admit subjects so that their first study vaccination occurs as close as possible to when the second dose of vaccine is indicated (i.e., 21 days after the first dose of the Pfizer-BioNTech vaccine and 28 days after the first dose of the Moderna vaccine), but since the goal of this study is to assess allergic reactions and not provide clinical vaccinations as indicated, subjects may be enrolled regardless of time elapsed since their initial vaccination. On day 1, they will be randomized at a 1:1 ratio to receive either placebo or the Pfizer-BioNTech vaccine. A pre-vaccination blood and urine sample will be obtained, and then the first dose (per randomization) of study vaccine will be given. Serial blood draws and the first void (urine) after the dose will be collected. Another post-vaccination void may be collected if an allergic reaction occurs after the first collection. The participant will be monitored by the principal investigator and/or an experienced allergist associate investigator for signs and symptoms of an allergic reaction and any other AE for a minimum of 3 hours, and medications and equipment will be immediately available to treat possible reactions. If a reaction does develop, the participant will be treated according to our study MOP, and additional urine samples may be collected to assess the immune response. If a skin rash develops, photographs may be taken to document variations in presentation. In case of a reaction after the first dose, the participant will be counseled and the second study vaccination will proceed as scheduled if the participant is willing. On day 2, the participant will receive either placebo or the Pfizer-BioNTech vaccine (whichever was not given on day 1) using the same procedure, but in the opposite arm. The participant will be monitored and treated (as needed) for an allergic reaction or AEs and samples will be collected as described for day 1. Participants will be discharged on day 3, unless they require additional treatment due to a reaction. Additionally, day 2 dosing may be delayed to a later day at the discretion of the investigator if the participant experiences an allergic reaction on day 1 that has not resolved by day 2 and does not rise to the level of a pausing or halting criterion (see sections 8.4.5 and 8.4.6). Day 2 dosing may be delayed for a maximum of 1 week. If the participant experiences other AEs (nonallergic in nature) on day 2 that are expected from the vaccine based on data from the Phase 3 trials (e.g. fatigue, headache, fever, myalgia), then the second study vaccination may still be given on day 2 as scheduled. A participant may be moved to a general ward after the completion of their vaccinations and close monitoring, when safe to do so.

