9.4 STATISTICAL ANALYSES

9.4.1 General Approach

Most analyses will result in estimates of binary endpoints and will be presented as proportions and corresponding exact 95% confidence intervals.

Exploratory endpoints, such as mechanistic endpoints, will be presented as means with standard deviations and/or as medians and interquartile ranges. Graphical presentation may be useful.

While hypothesis testing is likely to be limited in scope, two-sided p-values with alpha=.05 will be used, with appropriate cautions regarding interpretation due to multiplicity.

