9.4.3 Analysis of the Secondary Endpoint(s)

Analyses to simple single proportion estimates will follow the same approach described for the primary endpoint.

Analysis of risk difference between active and placebo vaccines will be addressed in 2 separate ways. First, using only data from the first study vaccination, the risk difference will be estimated (proportion with systemic reaction in the active vaccine arm minus the analogue in the placebo arm) with an unconditional exact confidence interval. The second approach will exploit the crossover design (i.e., comparing each individual's active vaccine to placebo response), by estimating the risk difference using a McNemar's approach to an exact confidence interval.[\[34\]](#) While the McNemar's approach should be more precise than the group comparison approach at the first study vaccination, the potential for missing data on the second study vaccination, especially in the initial vaccine arm is not ideal. If there are such missing data, the second study vaccination will be imputed in the most extreme ways (i.e., smallest risk difference and largest risk difference) to see if the results are robust.

Hypothesis testing can be done for the active vaccine versus placebo risk difference. A Fishers exact test will be done when comparing the randomized arm at the first study vaccination. An exact McNemar's test will be done when comparing the within-subject differences. Approaches to missing data for McNemar's follow the estimation approaches.

A signed rank test will also be done to compare severity of reaction at the first vaccine (i.e., done prior to enrollment) to active study vaccine (where the difference in grade is the metric). Since that analysis assumes grade is linear, these data will also be analyzed using a purely ordinal approach to grade using a longitudinal GEE model with a cumulative logit link; this is effectively a generalization of McNemar's test, but for ordinal instead of binary data. Tabular data will also be presented.

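### Table 6, 1.00 vaccine / .00 placebo column: the lower limits at N=80 and N=100 (0.702, 0.597) should be 0.910 and 0.928, and once corrected Table 7 is not narrower anywhere in this column

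*Combined protocol and SAP*

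**What the plan says.** Section 9.2 uses example exact intervals in place of a power calculation and says that "the study will provide more precise estimates with greater enrollment". Table 6 is headed "Exact 95% Confidence Intervals for the Difference in Reaction Rate Between Vaccine and Placebo Arms on Day 1". Its first results column, "1.00 Vaccine, .00 Placebo", prints these lower limits, each with an upper limit of 1: 0.082 (N=6), 0.383 (10), 0.663 (20), 0.824 (40), 0.881 (60), 0.702 (80) and 0.597 (100).

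Table 7 gives the within-subject intervals. In the same column its lower limits are 0.338 (N=10), 0.621 (20), 0.797 (40), 0.861 (60), 0.895 (80) and 0.915 (100), and it also has rows for N=5 and N=15. The text after Table 7 states: "The confidence intervals in this table are narrower than the ones in the previous table, since they use information from both study vaccinations".

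Section 9.4.3 plans both analyses. The first-vaccination risk difference is to be reported "with an unconditional exact confidence interval", and the crossover risk difference with an exact interval of McNemar type.

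**The concern.** With observed rates held at 100% and 0%, more participants should narrow the interval. In this column it narrows up to N=60 and then widens. At N=100, the enrolment goal, the printed width of 0.403 exceeds the 0.379 printed for the less extreme .80/.20 scenario in the same row.

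The stakes are modest. Section 9.2 offers these tables as its evidence of achievable precision, and in this column precision appears to worsen as enrolment approaches the goal. At N=80 and N=100 the same cells also reverse the comparison between the two approaches planned in Section 9.4.3. If the routine behind Table 6 is used again for the final first-vaccination interval, the fault could recur where separation between the arms is nearly complete.

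**Working it through.** **Inputs.**
- 95% two-sided interval, so 0.025 per tail (Table 6 heading; Section 9.4.1).
- Equal arms, n = N/2 (1:1 randomisation in Section 4.1; the worked example in Section 9.2 has 10 per arm at N=20).
- Observed data n/n reactions on vaccine and 0/n on placebo (column heading).
- Unconditional exact method (Section 9.4.3).

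**Formula for Table 6.** All against none is the most extreme table possible, so any sensible ordering leaves it alone in the tail. With true placebo rate p and true difference d, its probability is (p+d)^n × (1−p)^n. This is largest at p = (1−d)/2, where it equals ((1+d)/2)^N. Setting that to 0.025 gives

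d = 2 × 0.025^(1/N) − 1.

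| N | 0.025^(1/N) | Lower limit | Printed |
|---|---|---|---|
| 6 | 0.5407 | 0.0815 | 0.082 |
| 10 | 0.6915 | 0.3830 | 0.383 |
| 20 | 0.8316 | 0.6631 | 0.663 |
| 40 | 0.9119 | 0.8238 | 0.824 |
| 60 | 0.9404 | 0.8807 | 0.881 |
| 80 | 0.9549 | 0.9099 | **0.702** |
| 100 | 0.9638 | 0.9276 | **0.597** |

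The first five rows reproduce the plan's figures to within 0.001. The last two do not.

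**Tail probability at the printed limits.** It should be 0.025.
- N=80: ((1+0.702)/2)^80 = 0.851^80 = 2.5 × 10⁻⁶.
- N=100: ((1+0.597)/2)^100 = 0.7985^100 = 1.7 × 10⁻¹⁰.

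**Other constructions.** Tail areas of 0.05 or 0.005, separate Clopper-Pearson limits per arm (0.025 or 0.0125 each), and square-and-add of Clopper-Pearson limits give 0.793 to 0.927 at N=80 and 0.832 to 0.941 at N=100. None gives 0.702 or 0.597.

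**Check of Table 7, same column.** When all N pairs are discordant in favour of vaccine, the lower limit is the 0.025 quantile of W(2T−1), with W and T independent Beta(N,1) and W set to 1 where T is below 0.5. This gives −0.044 (N=5), 0.338 (10), 0.517 (15), 0.621 (20), 0.797 (40), 0.861 (60), 0.895 (80) and 0.915 (100). All eight match print, so the comparison rests on a sound Table 7 column.

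**Widths in the 1.00/.00 column (1 minus the lower limit).**

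| N | Table 6 printed | Table 6 correct | Table 7 |
|---|---|---|---|
| 10 | 0.617 | 0.617 | 0.662 |
| 20 | 0.337 | 0.337 | 0.379 |
| 40 | 0.176 | 0.176 | 0.203 |
| 60 | 0.119 | 0.119 | 0.139 |
| 80 | 0.298 | 0.090 | 0.105 |
| 100 | 0.403 | 0.072 | 0.085 |

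As printed, Table 7 is narrower only at N=80 and N=100. After correction it is wider at all six shared N. In the .80/.20 and .60/.20 columns Table 7 is narrower at every shared N, for example 0.838 against 1.045 and 0.826 against 1.126 at N=10.

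**Possible cause (inferred; the documents name no software, ordering or tolerance).** Ordering tables by one-sided Fisher p-value, and treating p-values within an absolute 2.2 × 10⁻¹⁶ of the observed one as ties, gives 0.824, 0.881, 0.702 and 0.597 at N=40, 60, 80 and 100, with 1, 1, 23 and 80 tables in the tail. With zero tolerance only the observed table is in the tail, and the last two limits become 0.910 and 0.928.

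**The case against.** The case for treating this as trivial is fair in several respects. The tables are illustrative, and enrolment is up to 100 with no precision target. The primary analysis is a Clopper-Pearson interval, and the wrong intervals are too wide rather than too narrow and still exclude zero comfortably. Universal reaction to vaccine with none to placebo at N=80 or more is a boundary case; the case series in Section 2.3.3 reports potentially allergic symptoms in 20% of 159 patients at the second dose. Section 4.1 also records that by 15 September 2022 only two participants had still to complete the month-5 visit, so the planning use of the table appears largely past. All of this stands and keeps the point small.

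The recurrence risk rests on an inferred cause. Under that cause the tolerance changes no lower limit in the .80/.20 or .60/.20 columns at N=40 to 100, so the risk is confined to near-complete separation in larger samples. That also stands. Because the inferred rule returns both anomalous values, a check is still worth making.

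It can also be said that the sentence about narrower intervals follows a .80/.20 example and holds in two of the three columns. But it is worded for the whole table, and in the remaining column it already fails at N=10 to 60 as printed, independently of the two cells.

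Finally, two should not be read as a complete count of errors in Table 6. At N=10 in the .60/.20 column the printed lower limit is −0.268, whereas ordering by simple difference or by one-sided Fisher p-value gives −0.305. Ordering by simple difference also gives 0.353, 0.391 and 0.416 at N=60, 80 and 100 in the .80/.20 column, against 0.313, 0.338 and 0.355 printed. Those columns depend on an ordering that the plan does not name, so these differences are not claimed as errors here, but they support re-running the table.

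**Conclusion.** The concern holds. The lower limits 0.702 and 0.597 are wrong; the values are 0.910 and 0.928. The printed intervals are about 3.3 times too wide at N=80 (0.298/0.090) and 5.6 times at N=100 (0.403/0.072). The unrestricted statement that Table 7 is narrower is false in the 1.00/.00 column at four of the six shared N as printed, and at all six once corrected.

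This rests on equal arms, 0.025 per tail and the unconditional exact method, all stated in the plan. It does not rest on the choice of ordering statistic, because the observed table is the extreme one, nor on the inferred software cause. The enrolment goal, the decision rules and the primary analysis are unaffected. It is a limited correction that should be made.

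**What to change.** 1. In Table 6, 1.00/.00 column, print 0.910–1 at N=80 and 0.928–1 at N=100.
2. Re-run the whole of Table 6 and state the ordering statistic and the tie rule.
3. Reword the sentence after Table 7 to say that its intervals are narrower than those of Table 6 in the .80/.20 and .60/.20 scenarios but not in the 1.00/.00 scenario.
4. Before producing the first-vaccination interval of Section 9.4.3, check the routine against 2 × 0.025^(1/N) − 1 at N=80 and N=100. Compare very small p-values on a relative or log scale that still recognises genuine ties.

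The cost is two cells, one sentence, one stated rule, a re-run of one table and a short software check. If the re-run changes other cells of Table 6, they should be updated at the same time. Nothing in the conduct of the trial changes.
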